7.9 Adverse Events, Serious Adverse Events and Post Injection Reactions

Adverse Event (AE) Definition: An AE is any untoward medical occurrence in a participant to whom a medicinal product has been administered, including occurrences which are not necessarily caused by or related to that product. An AE can therefore be any unfavorable and unintended sign (including an abnormal laboratory finding), symptom, or disease (new or exacerbated) temporally associated with the use of a study intervention. An adverse event (AE) does not include medical or surgical procedures, although the condition that led to the procedure may be an AE, or situations where an untoward medical occurrence has not occurred (e.g. hospitalization for elective surgery, social and/or convenience admissions). Any medical condition or clinically significant laboratory abnormality with an onset date before baseline are considered to be pre-existing conditions and should be documented as medical history.

Adverse Drug Reaction (ADR): An adverse drug reaction is defined as a noxious and unintended response to a medication related to any doses where there is at least a reasonable possibility of a causal association between the medication and the AE, i.e. the relationship cannot be ruled out. All cases judged by either the reporting medically qualified professional or ViiV as having a reasonable suspected causal relationship to the drug qualify as adverse reactions. Note: Injection site reactions are considered drug related as they are related to the administration of Cabenuva.

Serious Adverse Event (SAE): A serious adverse event is any untoward medical occurrence that:

- results in death
- is life-threatening
- requires inpatient hospitalization or prolongation of existing hospitalization unless hospitalization is for:
 - Routine treatment or monitoring of the studies indication, not associated with any deterioration in condition.
 - Elective or pre-planned treatment for pre-existing condition that is unrelated to the indication under study and has not worsened since the start of the study drug.
 - Treatment on an emergency outpatient basis for an event not fulfilling any of the definitions of SAE given above and not resulting in hospital admission.
 - Social reasons and respite care in the absence of any deterioration in the patient's general condition.
- results in persistent or significant disability/incapacity
- consists of a congenital anomaly or birth defect

Protocol Title: **CAB-RPV LA Implementation Strategies for High-Risk Populations**

- is medically significant, i.e. defined as an event that jeopardizes the patient or may require medical or surgical intervention to prevent one of the outcomes listed above

The term “life-threatening” in the definition of “serious” refers to an event in which the participant was at risk of death at the time of the event; it does not refer to an event which hypothetically might have caused death if it were more severe. A serious adverse reaction (SAR) is an adverse event that is both serious and, in the opinion of the reporting Investigator, believed with reasonable probability to be due to the study product, based on the information provided. “Severe” is often used to describe intensity of a specific event, which may be of relatively minor medical significance. “Seriousness” is the regulatory definition supplied above. All SAEs whether related or not to Cabenuva will be collected in this study. Prompt notification to ViiV of an SAE is essential so that legal obligations and ethical responsibilities towards the safety of participants and the safety of Cabenuva are met.

Medical Device Deficiency/Incident Definition: A device deficiency/incident is an inadequacy of a medical device with respect to its identity, quality, durability, reliability, safety, or performance. These can include malfunctions, use errors, and/or deficiencies in information supplied by the manufacturer. Device deficiencies/incidents may result in an SAE (including death or serious deterioration in health of a participant or other non-participant person).

Assessment and Treatment of Adverse Events and Serious Adverse Events: Health care providers administering the injection and any qualified designees are responsible for detecting, documenting, and reporting events that meet the above definition of an AE or SAE from the time of the informed consent to study termination. Health care providers administering the injection should send all reported Adverse Events and Serious Adverse Events to the Principal Investigator and Study Clinician for follow up medical management and to determine relatedness to the injection. After the initial Adverse Event/Serious Adverse Event report, the study clinician or clinician administering the injection will proactively follow the participant at all subsequent injection visits and study contacts. All Serious Adverse Events will be followed until the event is resolved, stabilized, otherwise explained, or the participant is lost to follow-up.

Post-Injection Reaction: In the case of a post injection reaction, including, but not limited to, dyspnea, bronchospasms, agitation, abdominal cramping, rash/urticaria, dizziness, flushing, sweating, oral numbness, changes in blood pressure, and pain, participants will be monitored for 15 minutes post injection. Oxygen, epinephrine, intravenous fluids, corticosteroids, antihistamines and subcutaneous adrenaline will all be available on site at Project Trust. Offsite, epinephrine, corticosteroids, antihistamines and subcutaneous adrenaline will be brought with clinical staff. If participant's status indicates that they need oxygen, intravenous fluids, or their status is declining, emergency services will be called and the participant will be brought to the Boston Medical Center emergency department. While onsite at Project Trust, if a reaction lasts longer than 30 minutes, or the participant shows signs that their clinical condition is declining, emergency services will be called immediately.

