7.7 Missed Injection Target Dose Timeline

Protocol Title: **CAB-RPV LA Implementation Strategies for High-Risk Populations**

In order to ensure that patients receive their injection within the 7 days of their target injection date, the following outline will be followed. This outline is applicable for any missed dose:

- **Day 1 Post Target:** The study team will outreach to the participant via their preferred communication method as specified in their locator form in order to encourage them to return within the following three days. The encounter will be tracked in the study Log Book.
- **Day 3 Post Target:** The study team will outreach again to the participant via the preferred communication method to encourage them to return the following day. The encounter will be tracked in the study Log Book.
- **Days 5-7 Post Target:** The study team will enlist BMC's ARCH and PT street-based outreach workers who are experienced with and successful at reaching and engaging high-risk patients. The outreach workers will conduct active outreach to the participant in the community to bring them in for a visit. If active outreach is unsuccessful, the study team will also use the contacts on the locator form to attempt to reach the participant. The encounter will be tracked in the study Log Book.
- **Upon Return Within 14 Days Post Target:** The study clinician will obtain a viral load and genotype. If the participant's viral load is less than 200 copies per mL, they will administer the CAB-RPV LA. If the participant's viral load is over 200 copies per mL, the study clinician will refer them to their primary care provider who will make the determination about whether or not an injection is appropriate. The encounter will be tracked in the study Log Book.
- **If participant returns after 15 days Post Target:**
 - **Missed Dose Occurs within 2 months of Initiation Injection:** The participant will be given a maintenance dose at their next contact with study staff (400mg/600mg 2 ml). The participant will then resume their normally scheduled injection plan, i.e. next injection scheduled to be given 25-32 days after maintenance dose administered.
 - **Missed Dose Occurs after first 2 months of injection:** The participant will be given a loading dose instead of their scheduled dosing amount (600mg/900 mg 3 ml). The participant will then resume their normally scheduled injection plan.

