- All SAEs in participants exposed to the injection, regardless of Principal Investigator or clinician assessment of causality.
- All AEs considered related to Cabenuva, with the exception of certain non-serious local Injection Site Reactions (listed below)

Protocol Title: **CAB-RPV LA Implementation Strategies for High-Risk Populations**

- All medical device incidents with Cabenuva
- All pregnancies in participants exposed to the injection

Injection Site Reaction: Injection Site Reactions (ISR) are considered drug related events, as they are related to the administration of Cabeuva. Localized non-serious ISRs with Cabenuva (redness, itching, swelling, pain or discomfort) are well characterized as described in the USPI, as such, these events will not be reported to ViiV as part of the study. However, any ISRs meeting serious criteria (complications of ISRs such as cellulitis, abscess) will be reported to ViiV, using the SAE reporting form.

Post Injection Reaction: All suspected post injection reactions whether serious or non-serious will be reported to ViiV.

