10.0 Data Handling and Record Keeping

10.1 Confidentiality

At the screening consent appointment, participants will complete the HIPAA Authorization to grant permission to study staff to review their EHR. After an individual provides informed consent for screening and HIPAA authorization, a clinician will review their most recent labs for genotype and viral load, which would typically be part of standard care, to determine if they are eligible for CAB-RPV LA. Results of this review will be used to determine final eligibility. Following this, the EHR will be reviewed at 3 months and 6 months to document information needed to evaluate outcomes using the Chart Review Form. Other clinical and demographic information will also be abstracted to enable investigators to better characterize the study sample and to use as covariates in analyses. There will be no additional clinical records kept specifically for the study. As CAB-RPV LA is one standard of care for HIV, record of injections received will also be recorded in the EHR. All study data will be stored on a secure, password protected computer. Additionally, although no personal or identifiable data will be collected beyond the informed consent form, all documents created, such as those related to analyses and findings, will be maintained in a locked filing cabinet and in a password-protected database only accessible to the researchers.

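### The plan commits to collecting all SAEs but does not say how a first SAE would be found in a participant who stops attending

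*Combined protocol and SAP*

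**What the plan says.** **What is promised.** Section 7.9 states: "All SAEs whether related or not to Cabenuva will be collected in this study". Section 8.1 lists among the events to be documented: "All SAEs in participants exposed to the injection, regardless of Principal Investigator or clinician assessment of causality". The window in both sections is "from the time of the informed consent to study termination", so the commitment does not lapse when a participant stops injections.

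**Who detects.** Section 7.9, repeated almost word for word in 8.1: "Health care providers administering the injection and any qualified designees are responsible for detecting, documenting, and reporting events".

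**What follows a report.** Once a first event has been reported, the study clinician or injecting clinician "will proactively follow the participant at all subsequent injection visits and study contacts" (Section 7.9). SAE follow-up runs to resolution, stabilisation or another explanation, "or the participant is lost to follow-up".

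**What else brings staff into contact with participants or their records.** Section 7.7 sets out tracing after a missed injection, including on days 5-7: "The outreach workers will conduct active outreach to the participant in the community to bring them in for a visit". Sections 6.0 and 7.3 schedule midpoint and endpoint surveys for all cohorts. Section 7.11 keeps participants in usual infectious disease care. Section 9.0 says medical events related to HIV disease are collected and reviewed by the study clinician. Section 10.1 says "the EHR will be reviewed at 3 months and 6 months to document information needed to evaluate outcomes".

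**The concern.** The plan states complete ascertainment, names the responsible staff, and leaves the method open for the people least likely to be seen. Under the Section 7.9 definition an inpatient admission, with listed exceptions, makes an event serious. An admission is also a plain reason to miss an injection. The chance that an event is noticed can therefore depend on the event itself, which is the setting in which passive reporting undercounts.

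Section 4.1 names dropping out of care as the primary risk of participation, so the group concerned is one the plan expects. The treatment of missing information also differs by outcome. Section 11.3 counts a missing viral load as detectable, whereas an SAE that nobody hears of is in effect counted as no event. At stake is whether the final report can say that all SAEs in exposed participants were collected.

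**Working it through.** The plan gives no SAE rate and no ascertainment figure, so there is nothing of its own to reproduce. The check is a reading of each route, followed by a rough scale.

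**Step 1. Does any stated route find a first SAE in someone who has stopped attending?**

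| Route | Section | Stated purpose | Assigned to SAE detection? |
|---|---|---|---|
| Injecting providers and designees | 7.9, 8.1 | Detect, document and report | Yes, but no method given |
| Proactive follow-up | 7.9 | Follow a participant after a first report | No; it starts after detection |
| Missed-dose tracing: days 1, 3 and 5-7, then locator contacts | 7.7 | Bring the participant back for the injection | Not stated |
| Midpoint and endpoint surveys | 6.0, 7.3 | Sociodemographics, unmet needs, satisfaction, stigma | Not stated |
| Clinic care by infectious disease providers on the study staff | 7.11 | Clinical management, including of SAEs | Management only |
| HIV-related medical events | 9.0 | Collection and clinician review | Part of all SAEs; source not stated |
| Record review at 3 and 6 months | 7.3, 10.1 | Outcomes; appointment adherence, viral load and CD4 named, list left open | Not stated |

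Several routes could bring an admission to light. None is told to look for one.

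**Step 2. Scale in Cohort 1.** Inputs: 20 per cohort (Section 11.2); at least 80% begin injections (H1) and 80% of those complete six (H2), both in Section 11.1.

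- Starters, that is, exposed to the injection: 20 × 0.80 = 16.
- Starters who do not complete: 16 × 0.20 = 3.2.

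Not all of these 3.2 stop attending. In the Section 7.0 regimen table a Cohort 1 participant on the bi-monthly schedule is injected in months 1, 2, 4 and 6 (no lead-in) or months 2, 3, 5 and 7 (lead-in). That is four injections, so someone can attend throughout and still not reach six. The 3.2 is a planning figure for people at risk of being lost from view, not a forecast.

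**Step 3. Events at risk of being missed.** Assumed risk of an SAE-qualifying admission among those who stop: 10% to 30% (not in the documents). Expected missed = 3.2 × risk × (1 − share found by other routes).

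| Share found by other routes | Risk 10% | Risk 20% | Risk 30% |
|---|---|---|---|
| None | 0.32 | 0.64 | 0.96 |
| Half | 0.16 | 0.32 | 0.48 |
| All | 0 | 0 | 0 |

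If all 20 start, 20 × 0.20 = 4 do not complete, and the top row becomes 0.4, 0.8 and 1.2.

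**Step 4. Weight of one event.** 1/16 = 6.25%, about 6 percentage points of those exposed in Cohort 1 (1/20 = 5 points if all start).

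The plan sets no retention target for Cohort 2, so no parallel figure can be derived there. The gap in method is the same.

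**The case against.** The strongest reply is that detection is not confined to injection visits. Section 7.9 includes qualified designees and a window that runs to study termination. Injecting clinicians are hospital staff (Section 6.0). Participants new to the hospital are placed on the panel of a study-staff infectious disease provider (Section 7.11), so stopping injections need not end contact with a study clinician. Tracing, locator contacts and surveys do not depend on an injection being given. The list of record items in Section 7.3 is open-ended, and the Chart Review Tool (Appendix E) is not in the reviewed text; it may already carry admissions.

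Most of this stands, and it limits the point to events that may be missed. It does not close the gap, because no section tells any of these routes to look for SAEs.

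Three stronger readings are tempting and are not supported:

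- **That SAEs in people who stop will be missed.** This needs every other route to fail, and the documents do not show that.
- **That 7 of 20 participants are affected.** 20 × (1 − 0.80 × 0.80) = 7.2 includes 4 who never start and so fall outside the exposed group in Section 8.1.
- **That the community site would look safer than the clinic.** The Section 7.9 wording is not limited to Cohort 1, Cohort 2 has the same gap, and neither the hypotheses in 11.1 nor the methods in 11.3 compare SAEs between sites.

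**Conclusion.** The point holds as a gap in method: complete SAE collection is promised, and no stated procedure finds a first SAE in an exposed participant who stops attending. Under-ascertainment is possible and would be related to the event. It affects the absolute SAE count in Cohorts 1 and 2; no direction between sites is shown.

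The size is small in number: about 0.3 to 1.0 events in Cohort 1 if no other route finds any, and fewer if tracing or record review does. This rests on the H1 and H2 targets being met exactly, on non-completion as a generous stand-in for ceasing to attend, and on an assumed 10% to 30% risk. With about 16 exposed, one event would still be visible in the reported rate. This is a worthwhile improvement, not a flaw that undermines the study.

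**What to change.** In Sections 7.9 and 8.1, state that at each scheduled 3- and 6-month record review, hospital admissions and deaths since the last review are recorded for every participant exposed to CAB-RPV LA (Cohorts 1 and 2), including those who have stopped. Pass them to the study clinician for SAE classification, since Section 7.9 excludes some admissions. Add the item to the Chart Review Tool if it is not already there.

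In the analysis, report SAEs over all exposed participants, split by whether they were still on injections or had stopped. State that admissions outside Boston Medical Center may not be captured; Section 7.1 allows Cohort 1 recruits whose care is elsewhere.

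The cost is low: the authorisation, record access and both reviews are already in Section 10.1. The downside is a few more SAE forms and a less favourable SAE count. Events after the 6-month review would still rely on the existing route.

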7.10 Accidental IV Administration

In the event of a suspected accidental IV administration, clinical staff will monitor participant's viral load within 2 weeks of IV administration.

7.11 Clinical Management of Participants

Many patients will already be Boston Medical Center patients, and will continue to see their usual Infectious Disease provider during the entirety of the study. Clinical decisions

Protocol Title: **CAB-RPV LA Implementation Strategies for High-Risk Populations**

around patients and the clinical management of missed doses, serious adverse events and adverse events will be managed by the Infectious Disease clinical providers who are on the study staff. Participants who are new to Boston Medical Center will have a new patient MRN assigned to them, and will be assigned to the clinical patient panel of one of the CID providers on the study staff. All clinical decisions about patients will be made by their healthcare providers. Whether to continue or discontinue Cabenuva if a participant becomes pregnant will be decided by the study clinicians in collaboration with the participant's CID provider that will also include a full review of the participant's case and medical record. All participants will continue to be offered all their regular services as before, including care in the CID, relapse prevention and harm reduction services, STI education and counseling, and all other needed services. Study staff will monitor for depression using the same procedures as CID.

8.0 Safety Reporting

8.1 Safety Reporting to ViiV

Healthcare providers administering the injection and any qualified designees are responsible for detecting, documenting, and reporting events that meet the definition of an AE or SAE from the time of the informed consent to study termination. As described in Section 7.9 above, healthcare providers administering the injection will send all reported AEs and SAEs to the Principal Investigator and the Study Clinician for follow up medical management and to determine relatedness to the injection. Treatment related to AE or SAEs will be recorded in the EHR and in the study logbook. ViiV will be informed of all these events. The Principal Investigator and the Study Clinician will be responsible for assessing AEs and SAEs for causality and for final review and confirmation of accuracy of event information and assessments.

All treatment-related Non-Serious AEs and Adverse Drug Reactions will be recorded in the "Non-Serious Adverse Event/Adverse Drug Reaction (AE/ADR) Pages" provided by ViiV. A blank, printed copy of this document will be kept in the locked filing cabinet along with the Log Book. Providers will be asked to fill out the document at the time that the Non-Serious AE occurs, and provide the document to the Principal Investigator who will fax the "Non-Serious Adverse Events/Adverse Drug Reaction (AE/ADR) Pages" document to ViiV within 5 days of the event occurring.

Assessment of Causality for Injection: The relationship of the injection to each AE will be assessed taking into consideration the following:

- A reasonable possibility is meant to convey that there are facts/evidence or arguments to suggest a causal relationship, rather than a relationship cannot be ruled out.
- The HIV clinician will use clinical judgment to determine the relationship.
- Alternative causes, such as natural history of the underlying diseases, concomitant therapy, other risk factors, and the temporal relationship of the event to the study treatment will be considered and investigated.
- The USPI for marketed products will be used in consideration of this assessment.

The terms to assess the relationship of an event to study agent are:

Related: There is a reasonable possibility an event may be related to Cabenuva.

Not Related: There is not a reasonable possibility an event is related to Cabenuva

Adverse Events to Be Documented in this Study:

- All AEs and SAEs considered to be related to oral CAB or oral RPV.
- All SAEs in participants exposed to the injection, regardless of Principal Investigator or clinician assessment of causality.
- All AEs considered related to Cabenuva, with the exception of certain non-serious local Injection Site Reactions (listed below)

Protocol Title: **CAB-RPV LA Implementation Strategies for High-Risk Populations**

- All medical device incidents with Cabenuva
- All pregnancies in participants exposed to the injection

Injection Site Reaction: Injection Site Reactions (ISR) are considered drug related events, as they are related to the administration of Cabeuva. Localized non-serious ISRs with Cabenuva (redness, itching, swelling, pain or discomfort) are well characterized as described in the USPI, as such, these events will not be reported to ViiV as part of the study. However, any ISRs meeting serious criteria (complications of ISRs such as cellulitis, abscess) will be reported to ViiV, using the SAE reporting form.

Post Injection Reaction: All suspected post injection reactions whether serious or non-serious will be reported to ViiV.

